### **Inclusion/Exclusion Criteria**

#### Inclusion Criteria:

- A child who attends a childcare center enrolled to Aim 1.
- A child who is  $\geq 3$  years and  $\leq 6$  years old

#### Exclusion Criteria:

- Parent/legal guardian is unwilling to provide written informed consent

### **Number of Subjects and Subject Timeline**

We plan to enroll up to 72 children. Each child will participate in the study for approximately 8 weeks. Surveys take parents about 20-30 minutes to complete. Anthropometric measures (height and weight) take about 5-10 minutes for each child to complete and will be performed at baseline and post-intervention (6-8 weeks follow-up). Fundamental motor skill competency testing will be performed at baseline and post-intervention (6-8 weeks follow-up) and will take approximately 30 minutes per child. Additionally, cognitive testing takes approximately 30 minutes for each child and will be performed at follow-up only. The child will be given an ActiGraph accelerometer to wear for 7 days at both baseline and post-intervention (6-8 week follow-up). An ActivPal accelerometer will also be distributed for the child to wear for 4 days at follow-up only. We plan to conduct all child visits between September 2018 and May 2018.

## Study Timeline

This project will occur from July 1, 2017, to July 1, 2019.

Table 1: Study Timeline		Weeks																	
		1	2	3	4	5	6	7	8	9	10	11	12	13	14	15	16	17	18
Recruitment/ Planning																			
Pre-Testing																			
Stenciling																			
Novel-effect Wait Period																			
Post-Testing																			

## Recruitment Methods

All parents of children between the ages of 3-6 years at the 4 selected childcare centers will receive an informational handout/flyer and consent form to participate in study procedures. Informational materials about the study may also be distributed to parents via email, mail, fax, phone, or in-person through the school. Children for whom a completed consent form is returned by their parent or legal guardian will be eligible to participate. We aim to recruit up to 72 children (18 per center) between August 2018 and February 2019.

## Consent Process

Parents/guardians will provide written consent for their child to participate in the study prior to data collection. The consent will include information about the study purpose, procedures, and timeline. Consent forms will be sent home with children and returned by parents to the childcare center staff. All children whose parents do not complete a written consent form within the given time will not be included in the study. Due to their young age, children will not provide formal assent, but will be notified that researchers will be present in the classroom. The full purpose of the study will not be disclosed to children at the childcare center until after the completion of all measurements and observations, so as to minimize the alteration of the children's behaviors.

## Procedures

Below are the procedures that will be completed during study participation (Table 2).

Table 2: Procedures and Timeframes				
	Baseline Intervention Center	Baseline Control Center	Follow-up Intervention Center	Follow-up Control Center
Consent	X	X		
Parent Survey	X	X		
Height	X	X	X	X

Weight	X	X	X	X
TGMD-3 (Motor Skills)	X	X	X	X
Actigraph (Physical Activity)	X	X	X	X
Ages and Stages (Motor Skills Questionnaires – 4 yr olds only)			X	X
activPAL (Physical Activity – 4 yr olds only)			X	X
Card Sort, Go/No-Go, [name] (Cognitive/Executive Function Tests – 4 yr olds only)			X	X

Parent survey. Parents will be asked to complete a questionnaire that will provide information on the child's sociodemographic characteristics, including sex, date of birth, and parents' marital status, highest level of education, family income, occupation, employment status, and the child's physical activity, sedentary time, screen time and sleep time. There are also questions pertaining to electronic screen device use by the parent/caregiver with the child. The final sections asks about the child's sedentary travel time and time spent outside. The poverty guidelines developed by the Department of Health and Human Services will be used as our measure of socioeconomic status. The child's movement behaviors are designed to align with the forthcoming WHO Guidelines. The questionnaire should take 15-20 minutes for the parent to complete.

COVID-19 Survey. Parents will be asked to complete a version of the Parent Survey related to the stay at home order that families were under due to the COVID-19 pandemic. The survey will be administered by phone when possible, and will be sent out via email using REDCap as an alternative.

Anthropometric measurements. Height and weight of each child will be measured in a private setting with children dressed in light clothing. Height will be measured to the nearest 0.1 cm using a SECA portable stadiometer. The measure will be repeated and if the two measures differ by more than 0.5 cm a third measurement will be recorded. Weight will be measured to the nearest 0.1 kg using a SECA electronic scale. The measurement will be repeated and if the two measures differ by more than 0.25 kg a third measurement will be recorded. Body mass index (BMI) z-score will be calculated based on the child's age, sex, height, and weight, then compared to the 2000 Centers for Disease Control and Prevention (CDC) Growth Charts.

Physical activity. Physical activity and time spent in moderate to vigorous physical activity will be measured by a triaxial accelerometer (Actigraph GT3X+, Actigraph of Ft. Walton Beach, FL). Children will be measured by the Actigraph for 24 hours per day for 7 days. Measurements with the Actigraph will

occur for one week at baseline (before stenciling) and follow-up (6-8 weeks after stenciling). The child will be outfitted with the accelerometer on an elasticized belt, on the right mid-axillary line, and parents will be provided a handout with instructions on when and how to place the device on their child. The Actigraph is one of the most common accelerometers used for scientific purposes, and the GT3X+ version provides extensive data on steps/day and time spent in various activity intensities. During wear weeks, study staff will check accelerometry wear during school hours to assess for compliance. The minimal amount of accelerometer data that will be considered acceptable is 4 days. Following the final day of data collection, the research team will verify the data for completeness using the most recent version of the ActiLife software (version 5.6 or higher; ActiGraph, Pensacola, FL) available at the time. Established cut-points will be used to classify sedentary behavior and physical activity such as the criteria of Pate et al. sedentary 0-799 counts per minute (CPM), light 800-1679 CPM, moderate 168-3367 CPM, and vigorous  $\geq$  3368 CPM. Other cutpoints may also be used for analyses.

The activPAL is a small device worn on the thigh by a small piece of tape. The monitors capture physical activity, sedentary time (including posture) and sleep. Children will be encouraged to wear the activPAL continuously for at least 72 hours, up to 96 hours (i.e., not take it off for any reason, including water activities [bathing, swimming] and sleeping). The monitor will be placed on the child on the first day they attend follow up assessments at the center and removed 4 days later at the center. Measurements with the activPAL will occur for 72-96 hours at follow-up only, and parents will be provided with instructions on use as well as additional tape for applying the device. ActivPALs will be distributed only to enrolled 4 year olds.

Fundamental Motor Skill Assessments. The Test of Gross Motor Development - 3rd edition (TGMD-3) will be administered with the cooperation and support of the childcare center staff in small group settings. Groups of approximately 3-4 students will complete the assessments together. The TGMD-3 uses direct observation to evaluate performance on 13 skills including running, horizontal jumping, hopping, skipping, sliding, galloping, and balls skills (two-hand striking, one-hand striking, catching, kicking, overhand throwing, underhand throwing and dribbling). The TGMD-3 involves a trained administrator demonstrating the proper execution of the skill, and the participant is allowed one practice trial, then two formal trials that will be evaluated. These assessments will be video recorded. The TGMD-3 takes 20-25 minutes to complete each group.

Ages and Stages Questionnaire (ASQ-3). Staff will complete the 'Gross Motor Skills' and 'Fine Motor Skills' sections of the Ages and Stages Questionnaire. The ASQ-3 is a developmental screener that evaluates communication, gross motor, fine motor, problem solving, and personal-social development. The full ASQ-3 takes 10–15 minutes to complete and will be performed on 4 year olds only.

Executive Functions. Three tests of executive function will be administered to children: The Early Years Toolbox (EYT) Card Sort Task, EYT Go/No-Go Task and EYT '[name]. The EYT Card Sort Task is an iPad-based assessment of cognitive flexibility - the ability to flexibly shift attention. Children are presented with cards that vary along two dimensions (i.e., shape and color) and are asked to sort each card (i.e., red rabbits and blue boats) first by one dimension (e.g., color) and then, after a number of trials, by another dimension (e.g., shape). This game takes approximately 5 minutes to complete. EYT

Go/No-Go Task is an iPad-based assessment of ‘inhibition’ – the ability to control behavioral urges and impulses. Children are presented with fish and sharks and are instructed to tap the iPad screen whenever they see a Fish (‘catch the fish’) and refrain from responding when a Shark appears (‘avoid the sharks’). This game takes around 6 minutes to complete. EYT ‘[name] is an iPad-based assessment of ‘visual-spatial working memory’ – the amount of visual information that concurrently can be coordinated in the mind. Children are presented with an image of a cartoon character – [name] – who has a number of colored dots placed in different spatial locations on his body. After a predetermined amount of time, these dots disappear and the child is then asked to recall the locations of the dots by tapping the corresponding locations. EYT will only be performed on enrolled 4 year olds.

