The aim will be achieved through a pilot project that is grounded in rigorous and reproducible methodology, meaning the results can be generalized to other parts of the state and held as a model throughout the country. We expect that children who attend the childcare center that receives the stenciling will have greater increases in moderate to vigorous physical activity (MVPA) and fundamental motor skill competency, and larger decreases in sedentary behavior, compared to children who attend the control facility (who will receive the stencils after an approximate 6 to 8-week delay). The main outcome variable will be percentage of recess time spent in MVPA, measured objectively using a physical activity monitor (i.e. accelerometer). Additional outcome variables include fundamental motor skill competency, measured using the validated Test of Gross Motor Development (TGMD-3; Ulrich, 2016), and the percentage of recess spent being sedentary (accelerometry). Parents will provide demographics of all consented children, and height and weight will be collected before and after the intervention. We do not expect changes in weight status during this short time period but will include obesity as a covariate to control for differences in MVPA that may be due to weight.

This project will test the effectiveness of a promising (cost-effective, easily scalable) playground stenciling intervention in order to validate the need for dissemination to numerous childcare centers across Louisiana. Ultimately, this pilot may launch an innovative strategy that has the potential to disrupt negative trends in obesity and sedentary behavior among Louisiana preschoolers.

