## B. Background

The significance of this project stems from Louisiana's prevalence of preschool obesity which is 60% higher than the national average: 13.8% of preschoolers in the state are obese compared to 8.4% nationally. Physical activity during early childhood is known to reduce the risk of being overweight or obese and therefore protect against the development of comorbidities, such as heart disease, diabetes, etc. later in life. Furthermore, at this young age the development of fundamental motor skills is highly related to physical activity and is therefore an important correlate to obesity. Despite assumptions that young children are active throughout the day, studies indicate that almost half of preschool play time is spent in sedentary activities. Over 80% of children spend some time in childcare settings by the age of 3 years, making childcare facilities an important venue for the promotion of fundamental motor skills and physical activity. As playground stenciling has been shown to increase moderate to vigorous physical activity (MVPA) during recess among older children, it is necessary to determine whether it has the same benefit for preschool aged children. Therefore, we propose to use a scientifically rigorous design (intervention vs. wait-list control) to determine the effectiveness of playground stenciling in Louisiana preschool aged children, a population burdened with an urgent, established obesity epidemic.

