### **Primary Endpoints and Data Analysis Plan**

The primary endpoints include change in MVPA and sedentary time during recess measured by accelerometry. The secondary outcome includes change in fundamental motor skills.

Statistical analyses will be performed with the latest version of SAS. Means, standard deviations, and Pearson correlations will be calculated to describe the sample and examine differences between the intervention and control group. Differences in center characteristics (e.g. racial distribution of participants) will be tested using t-tests and chi-square tests. A repeated measures ANCOVA model will be used to test for effects of playground stenciling on each dependent continuous variable (minutes/recess MVPA, minutes/day MVPA in childcare center, minutes/recess Sedentary behavior, minutes/day Sedentary behavior in childcare center, minutes/day MVPA total, minutes/day screen-time total). T-tests and chi-square tests will be used to determine whether changes in outcome variables were different between the intervention and control childcare centers. Covariates will include age, sex, BMI z-score, and sociodemographic characteristics.

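### Does the four-day accelerometer rule need a recess-wear condition before the recess endpoints can be analysed?

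*Combined protocol and SAP*

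**What the plan says.** Under A. Specific Aims: "The main outcome variable will be percentage of recess time spent in MVPA". Under Primary Endpoints and Data Analysis Plan: "The primary endpoints include change in MVPA and sedentary time during recess measured by accelerometry". The same analysis section also lists outcomes per day in the center and per whole day.

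Under Procedures, in the physical activity text, the wear schedule is: "Children will be measured by the Actigraph for 24 hours per day for 7 days". This applies once at baseline and once at follow-up. The only acceptability threshold is "The minimal amount of accelerometer data that will be considered acceptable is 4 days". Two checks accompany it: "During wear weeks, study staff will check accelerometry wear during school hours to assess for compliance", and after collection "the research team will verify the data for completeness using the most recent version of the ActiLife software". Neither check carries an inclusion criterion. The cut-points place 0-799 counts per minute in the sedentary class.

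The section on privacy and safety monitoring describes the one-week wear differently, as covering the time the child is at the center.

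**The concern.** One day-count rule has to serve three outcome windows: recess, the day in the center, and the whole day. Only the last is naturally judged by days of wear. Two consequences suggest themselves.

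First, a child could have four accepted days with the monitor off at recess. Zero counts lie inside the sedentary band, so unless they are removed as non-wear they would raise recess sedentary time and lower recess MVPA, which are the two primary endpoints.

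Second, if weekend days count towards the four, a child with two center days and two weekend days is kept, while a child with three center days and no weekend day is dropped. The second child has more recess data than the first.

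At stake is whether entry to the primary analysis, and the scoring of unworn recess, could be settled after the data have been seen.

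**Working it through.** The documents give no figure behind the four-day rule, so there is nothing to reproduce. The check asks how far each consequence could move the endpoints.

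**1. Non-wear scored as sedentary: effect on level**

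Inputs: true sedentary share s = 50%, taken from B. Background ("studies indicate that almost half of preschool play time is spent in sedentary activities"), which concerns play time generally and not recess in these centers; n recess days, of which m are unworn (assumed).

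- Observed sedentary share = (s(n − m) + m)/n. With n = 5 and m = 1: (0.5 × 4 + 1)/5 = 60%.
- Observed MVPA = true MVPA × (n − m)/n = true × 0.80.
- Across all sessions, if a share f is unworn, the mean sedentary level rises by f(1 − s). For an assumed f of 2% to 10%, that is 1 to 5 points.

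**2. Effect on change, which is the endpoint**

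- Observed sedentary share = s(1 − f) + f.
- With the same f at both waves, change = [s₂(1 − f) + f] − [s₁(1 − f) + f] = (s₂ − s₁)(1 − f). The added f cancels.
- MVPA behaves alike: (v₂ − v₁)(1 − f).
- For f = 2%, a true 5-point change (chosen for illustration) reads as 5 × 0.98 = 4.9 points. For f = 10%, it reads as 5 × 0.90 = 4.5 points.

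If f differs between waves but not between arms, each arm's change is shifted. For example, with s = 50% at both waves and f going from 2% to 10%, the shift is (10 − 2) × 0.5 = 4 points. The shift is common to both arms. With equal true levels at baseline, the difference in change between arms is (true difference) × (1 − f₂), where f₂ is the follow-up share; this is again attenuation. Bias other than attenuation needs unworn recess to differ by arm, and nothing in the documents suggests that it does.

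**3. Day count**

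Assumptions, none of them in the documents: weekend days count, centers open Monday to Friday, and children below four days are excluded.

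- There are 35 ways to choose 4 days from 7. Of these, 5 hold four weekdays, 20 hold three (with one weekend day) and 10 hold two. These are counts of sets, not probabilities.
- With independent daily wear p on center days and q on weekend days, the chance per wave of being dropped with three center days is 10p³(1 − p)²(1 − q)². The chance of being kept with two is 10p²(1 − p)³q².
- At p = 0.8 and q = 0.5: 10 × 0.512 × 0.04 × 0.25 = 5.1%, and 10 × 0.64 × 0.008 × 0.25 = 1.3%.
- For p from 0.6 to 0.9 and q from 0.3 up to p, the ranges are 0.1% to 16.9% and 0.1% to 8.3%. They are too wide to support a conclusion.

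If wear is confined to time at the center, as the privacy and safety section has it, the weekend route does not arise.

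**4. What a recess-specific minimum would gain**

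Take at least 3 of 5 recess days as an example, with daily wear 0.8 on all days and 72 children.

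- Chance of passing one wave: 0.967 under 4 of 7 days, 0.942 under 3 of 5.
- Passing both waves, independent: 72 × 0.967² = 67.3 against 72 × 0.942² = 63.9.
- Passing both waves, fully correlated: 69.6 against 67.8.

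The example rule therefore keeps about 2 to 3 fewer children. The calculation also treats daily wear as if it were wear throughout recess, so a strict recess condition could cost more.

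**The case for a change.** The strongest case for a change is that the protocol claims rigorous and reproducible methods, and a reproducible primary outcome needs a stated rule for which recess data count. The school-hours check monitors compliance and has no threshold. The completeness check does not say what the data must be complete against. With at most 72 children in four centers, a few inclusion decisions could matter, and adding wording costs little.

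Most of this is accurate as description. The gap exists, and the two accounts of the wear period do not match. What does not stand is the step from silence to harm. Nothing says that zeros from an unworn monitor are kept as sedentary time; removing non-wear is the ordinary first step in processing accelerometer data. An outcome expressed per recess session is computed from sessions with the monitor on, so the analyst arrives at the sensible rule without being told. The staff checks fall in the hours when recess takes place and make undetected non-wear there less likely. The added wording would leave its key number to the study team, and it would need recess times to be recorded. The documents do not describe such recording, so the cost is not only wording.

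The mismatch over wear period does not alter the recess endpoints: both accounts have the monitor worn at the center, where recess happens. The whole-day MVPA outcome in the analysis section needs wear outside the center, which fits the Procedures account. The other statement reads as a slip in a passage about risk.

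**Conclusion.** The four-day rule is incomplete for recess outcomes, but this is a detail that analysts fill sensibly, and no change to the plan follows. If unworn recess were nevertheless scored as sedentary at an equal rate at both waves, change would be attenuated by 2% to 10% for an assumed unworn share of 2% to 10%. The 1-to-5-point shift applies to level, not to change. The weekend-day scenario is only a possibility, resting on three unstated conditions and on assumed wear rates. The documents give no frequency for either problem, and no difference between arms is shown. The conclusion assumes that non-wear is removed in routine processing and that any recess non-wear is similar in the two arms. The two descriptions of the wear period are a clerical mismatch with no effect on the recess endpoints.

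### The moderate band is printed as 168-3367 CPM, most likely 1680 with its final zero dropped; this is the plan's only numeric lower bound for MVPA, and no cut-point set is named as primary

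*Combined protocol and SAP*

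**What the plan says.** All references are to the combined protocol and SAP.

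- **Procedures, Physical activity paragraph.** The bands are "sedentary 0-799 counts per minute (CPM), light 800-1679 CPM, moderate 168-3367 CPM", followed by vigorous at 3368 CPM or more. They are introduced by "Established cut-points will be used to classify sedentary behavior and physical activity such as the criteria of" a cited validation study in preschool children. The paragraph then adds "Other cutpoints may also be used for analyses".
- **A. Specific Aims.** "The main outcome variable will be percentage of recess time spent in MVPA".
- **Primary Endpoints and Data Analysis Plan.** "The primary endpoints include change in MVPA and sedentary time during recess measured by accelerometry". The dependent variables listed for the repeated measures ANCOVA are "minutes/recess MVPA, minutes/day MVPA in childcare center, minutes/recess Sedentary behavior" and "minutes/day Sedentary behavior in childcare center, minutes/day MVPA total, minutes/day screen-time total".

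Neither of the last two sections gives a numeric threshold or names a cut-point set. The bands in Procedures are the only ones in the plan.

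**The concern.** There are two linked problems.

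The first is an error in the text. Intensity bands must be mutually exclusive for a minute of recess to be assigned to one class. A moderate band that starts at 168 CPM contains part of the sedentary band and the whole of the light band. The lower end of moderate is also the lower end of MVPA, so the misprint falls on the threshold of the main outcome. Applied literally, it would count light activity, and much of what the same sentence calls sedentary, as MVPA.

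The second is an open choice that remains after the digit is corrected. The printed set is given as an example and other sets are allowed without being named. Recess MVPA and recess sedentary time both depend on the set chosen. More than one version of each primary result could therefore be produced, with no stated order of priority among them.

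**Working it through.** **Inputs**, all from the Physical activity paragraph of Procedures: sedentary 0-799, light 800-1679, moderate 168-3367, vigorous 3368 and above (CPM).

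**Step 1: boundaries as printed.** For contiguous integer bands, the lower bound of each band minus the upper bound of the band below should be +1.

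| Boundary | Calculation | Result |
|---|---|---|
| Sedentary to light | 800 − 799 | +1 |
| Light to moderate | 168 − 1679 | −1,511 |
| Moderate to vigorous | 3368 − 3367 | +1 |

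Only the light-to-moderate boundary fails.

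**Step 2: size of the overlap as printed.**
- With sedentary (168 to 799): 799 − 168 + 1 = 632 values, and 632 / 800 = 79% of that band.
- With light (800 to 1679): 1679 − 800 + 1 = 880 values, the whole band.
- Total in two classes: 632 + 880 = 1,512 values.

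These are ranges of count values, not shares of recess time. The documents give no distribution of counts, so they cannot be turned into minutes.

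**Step 3: the value that restores contiguity.** The light upper bound plus one is 1679 + 1 = 1680. With 1680, the four bands have no overlaps and no gaps. The moderate band is then 3367 − 1680 + 1 = 1,688 values wide, against 3367 − 168 + 1 = 3,200 as printed; the difference is the 1,512 from Step 2.

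**Step 4: likely cause.** 168 × 10 = 1680. Of all ways to insert a single digit into 168, only a zero at the end gives 1680. A dropped final zero is therefore the most likely explanation, and it can be inferred without the cited paper.

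**Step 5: what depends on the bound.** Of the six dependent variables in the analysis plan:
- three are MVPA (recess, childcare day, total day) and would take the misprinted bound if this set were applied;
- two are sedentary (recess, childcare day) and would use 0-799, which shows no internal inconsistency;
- one is screen time, which uses no band.

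**The case against.** The strongest reply is that the digit error corrects itself. Light ends at 1679 in the same sentence, and the bands restate a cited source, so a careful scorer would recover 1680. That is probably right, and it is why no bias is claimed. It does not remove the need to correct the only printed lower bound for the main outcome, which should not be left to inference.

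Four further objections have some force:

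- **Text conversion.** The text reviewed was read from a PDF by a program, so a digit lost there cannot be fully excluded. The neighbouring figures read cleanly, which makes this less likely. If the PDF shows 1680, the digit point falls and the point about naming a set stands.
- **The set is only an example.** No variable is formally tied to it, so the count of three out of six is conditional on its being applied. This is fair, but the lack of a formal tie is itself the second problem.
- **The sedentary band.** That it meets the light band shows internal consistency only; the documents cannot confirm 0-799 against the source.
- **Other scoring choices.** The device is described as triaxial, but neither the epoch length nor the axis to which the counts apply is stated. Correcting the digit and naming the set leaves those open.

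It can also be said that this is a pilot and that the named set is the natural default. Both are true, and one sentence would turn that default into a stated rule.

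**Conclusion.** The concern holds. As written, the moderate lower bound is wrong: 168 CPM is one tenth of the contiguous value (168 / 1680 = 0.10), a gap of 1680 − 168 = 1,512 CPM, and the printed bands cannot be used as exclusive categories. The dropped-zero explanation is an inference from the printed light band and should be checked against the cited study. The conclusion assumes that the published PDF carries the same figure as the text reviewed.

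The misprint does not show that any result is biased. It would affect results only if 168 had been entered in the scoring software, and the documents do not say what was entered. The unnamed primary set is less visible but bears on both primary endpoints and survives the correction. Together the two points should be fixed, at very little cost.

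**What to change.** 1. Check the figure in the PDF and in the cited validation study, then correct the moderate lower bound to 1680 CPM.
2. Add a sentence stating that this set defines the primary recess MVPA and recess sedentary endpoints, and that results from any other cut-points are sensitivity analyses.
3. Confirm the bound held in the scoring software.
4. If data have already been scored, record which set was applied and when it was chosen. This is possible: the Study Timeline says "This project will occur from July 1, 2017, to July 1, 2019", while the COVID-19 Survey paragraph of Procedures refers to a stay-at-home order in the past tense. The documents do not say whether scoring has taken place.

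The cost is one figure, one or two sentences and a check of a software setting, plus a short record if scoring is complete. MVPA would need re-scoring only if the check showed that 168 had been entered.

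This does not settle a separate difference: the Specific Aims express the main outcome as a percentage of recess time, while the analysis plan uses minutes per recess.

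### TGMD-3, the observer-rated secondary outcome, has no stated scoring source and no stated masking of scorers to arm or visit, although the sessions will be on video

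*Combined protocol and SAP*

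**What the plan says.** **Role of the outcome.** Under Primary Endpoints and Data Analysis Plan, "The secondary outcome includes change in fundamental motor skills". The same section plans t-tests of whether changes in outcome variables differ between intervention and control centers.

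**How it is measured.** Under Procedures, Fundamental Motor Skill Assessments, "The TGMD-3 uses direct observation to evaluate performance on 13 skills". Further, "The TGMD-3 involves a trained administrator demonstrating the proper execution of the skill"; the child has one practice attempt, "then two formal trials that will be evaluated". The test "will be administered with the cooperation and support of the childcare center staff in small group settings", with about 3-4 children per group. Then: "These assessments will be video recorded". Table 2 places the test at baseline and follow-up in both arms.

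**What the team expects.** A. Specific Aims predicts that children at the stenciled center "will have greater increases in moderate to vigorous physical activity (MVPA) and fundamental motor skill competency" than control children.

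**What is not stated.** The available text does not say who assigns the scores, whether scoring is live or from video, what the recordings are for, whether scorers know the center or the visit, or whether agreement between raters is checked. The only concealment described, under Consent Process, is that children are not told the full purpose. Data Management and Confidentiality gives one laboratory primary responsibility for collection, management, entry and analysis, and mentions no separate scoring team.

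**The concern.** Scoring a child's running, hopping or throwing by observation requires judgment. The plan states a directional hypothesis for this outcome, and testing takes place at the centers. If the person scoring knows that a session is the follow-up at a stenciled center, an expectation of improvement can raise borderline ratings there and not elsewhere. The planned covariates (age, sex, BMI z-score, sociodemographic characteristics) carry no information about this and cannot separate it from a real effect.

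The means of preventing it is already in the plan, because the sessions are recorded. The plan attaches no scoring use to the recordings. At stake is how far a motor-skill result, part of Aim 1, can be believed.

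**Working it through.** The plan has no figure to reproduce on this point: it gives no significance level, power, effect size or SD.

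**Step 1. Which rating errors matter.** Suppose scorers shift ratings between baseline and follow-up by d_S in the stenciled arm and d_C in the control arm (additive shifts). Then

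observed difference in change = (true change_S + d_S) − (true change_C + d_C) = true effect + (d_S − d_C).

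- If d_S = d_C, the shift cancels.
- If scorers cannot tell the visit, their leaning cannot depend on it, so d_S = d_C = 0 in expectation, even if they recognize the center.
- If scorers can tell the visit but not the arm, d_S = d_C and the shift cancels.
- The bias needs knowledge of both, at least in part. Masking to visit is therefore valuable by itself, because the outcome is a change.

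**Step 2. What could break the masking on film.**
- Stencils in frame would reveal arm and visit together, since the control centers are stenciled only after the delay.
- The activPAL is worn at follow-up only, by 4-year-olds only, and goes on at the first day of follow-up assessments. If visible, it reveals the visit but not the arm.

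**Step 3. Illustration of size.** Inputs: up to 72 children, 18 at each of 4 centers (Recruitment Methods; 18 × 4 = 72). Assumptions not in the documents: 36 v 36 children (two centers per arm, full enrolment, no losses), two-sided 5% level, no true effect, no clustering, and differential shifts b = d_S − d_C of 0.1, 0.2 and 0.3 SD of the change score.

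SE = √(2/36) = 0.236 SD. Rejection probability = Φ(b/SE − 1.96) + Φ(−b/SE − 1.96).

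| b (SD) | b/SE | Probability of a significant result |
|---|---|---|
| 0 | 0 | 5.0% |
| 0.1 | 0.424 | 7.1% |
| 0.2 | 0.849 | 13.6% |
| 0.3 | 1.273 | 24.7% |

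**Step 4. Sensitivity to clustering.** Take an intraclass correlation of 0.05 for the change score (assumed). The design effect is 1 + 17 × 0.05 = 1.85, and the true SE is 0.236 × √1.85 = 0.321 SD.

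- *Child-level test ignoring centers.* The critical value in true-SE units is 1.96/√1.85 = 1.441, so about 15% of tests are significant with no rater bias. With b = 0.2, b/SE = 0.624 and the rate is Φ(0.624 − 1.441) + Φ(−0.624 − 1.441) ≈ 23%.
- *Center-level t-test on four center means.* With 2 degrees of freedom the critical value is 4.303. With b = 0.2 (noncentrality 0.624) the rate goes from 5% to about 7%.

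The added false-positive risk from a 0.2 SD shift is thus about 9 percentage points (5% to 14%) without clustering, about 8 (15% to 23%) in a child-level test with clustering, and about 2 (5% to 7%) in a center-level test. In every case the estimate itself is shifted by the full b.

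**The case against.** The strongest reply is that the evidence is silence. A reader might infer that the scorers are unmasked, or that the administrator scores live while able to see a painted playground. The documents do not support either reading. Procedures says that the test uses direct observation and, separately, that an administrator demonstrates the skills. It does not say that this person scores, that scoring is live, or that testing is in view of the playground. Recording the sessions is also consistent with an intention to score from video. This stands, and it limits the point to what is unspecified.

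A reader might also infer that any bias would be permanent. That does not follow either: while the recordings exist, coded rescoring remains possible. Data are to be kept for 5 years after completion, although the plan does not say whether that covers the videos. What cannot remove the bias is further analysis of scores assigned without masking.

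Three other objections have weight:

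- The shifts are assumed, and ignoring clustering matters with four centers, as Step 4 shows. The percentages illustrate the mechanism and do not estimate its size.
- Video scoring takes work. At full enrolment it is 72 children × 13 skills × 2 trials × 2 visits = 3,744 trials, filmed in groups in which each child must be identified. The number of available raters is not given.
- This is a pilot, and only a secondary outcome is affected.

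These lower the priority. They do not remove the gap: an observer-rated outcome with a stated directional expectation has no stated protection against rater expectation.

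**Conclusion.** The point holds in a limited form. The plan specifies neither the source of the TGMD-3 scores nor any masking of scorers to arm or visit, although the sessions will be recorded. Only a rating shift that differs by arm would bias the comparison of change; a shift shared by both arms cancels. The accelerometer-based primary endpoints are unaffected.

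The size is unknown. Under the assumptions in Step 3, differential shifts of 0.1 to 0.3 SD of the change score would raise a 5% false-positive rate to between about 7% and 25%. Under clustering the starting rate and the increase would both differ. The documents do not show that scoring will be unmasked or that bias will occur. The change is worth making because it strengthens the outcome with recordings already planned.

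**What to change.** State in Procedures, Fundamental Motor Skill Assessments, that the TGMD-3 scores used for analysis come from the video recordings, and specify:

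1. Each recording is relabelled with a code that does not reveal center, arm or visit.
2. Existing trained staff score the coded recordings in random order, mixing baseline with follow-up and both arms.
3. Where possible, the scorer did not test children at that center.
4. Where possible, filming keeps stencils out of frame, and the activPAL is out of view or not yet fitted.

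If video scoring is already intended, only the coding, order and masking need to be added. If sessions have already been scored without masking, retained recordings could be rescored in this way.

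**Cost.** Relabelling files and preparing a random list is minor. The main cost is rater time, including telling apart the 3-4 children in each group recording. Scoring must wait until the follow-up videos are in. Masking may remain incomplete where the setting, stencils or activPAL can be recognized, and the report should say so. No measurement beyond the planned recording is needed.
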